11.5 Audit and inspection

The physician will permit study-related audits by auditors mandated by UCB Pharma and inspections by domestic or foreign regulatory authorities, after reasonable notice.

The main purposes of an audit or inspection are to confirm that the rights and well-being of the patients enrolled have been protected, that enrolled patients (ie, those signing consent and undergoing study procedures) are appropriate for the study, and that all data relevant for the evaluation of CZP have been processed and reported in compliance with the planned arrangements, the observational plan, physician's site, and IEC SOPs, and applicable regulatory requirements.

Confidential Page 34 of 89

The physician will provide direct access to all study documents, source records, and source data. If an inspection by a regulatory authority is announced, the physician will immediately inform UCB Pharma (or designee).

12 STATISTICS

A description of statistical methods is presented below and will be described in more detail in the Statistical Analysis Plan.

12.1 Definition of analysis sets

The analysis set for the efficacy variables will be the Full Analysis Set. The Full Analysis Set is defined as all patients with a DAS28 ≥2.6 who took at least one dose of CZP and had at least one valid post-Baseline DAS28 value.

Note: the Full Analysis Set is defined in this way because patients who had a Baseline DAS28 value <2.6 would already be in remission. Therefore, the primary efficacy variable to reach clinical remission would not be defined.

The analysis set for the safety variables will be the Safety Set (SS), which is defined as all patients who took at least one dose of CZP.

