4.1.3 Other efficacy variables

- Clinical remission (DAS28 of <2.6) by visit
- Low disease activity (DAS28 of \leq 3.2) by visit
- Proportion of patients achieving clinical response to treatment based on DAS28 reduction of ≥1.2 by visit
- Change from Baseline CDAI by visit
- Change in patient's arthritis pain as measured by Patient's Assessment of Arthritis Pain VAS by visit
- Change from Baseline in patient's fatigue as measured by Fatigue Assessment Scale by visit
- Change from Baseline in patient's physical function as measured by the HAQ-DI (Fries et al, 1980 and Lautenschläger et al, 1997) by visit
- Change from Baseline in health-related QoL measured as EQ-5D by visit, using the VAS part of the EQ-5D.
- Change from Baseline in quantity of concomitant DMARDs
- Change from Baseline in quantity of concomitant corticosteroids
- Incidence of discontinuation of CZP treatment due to DAS28 (CRP) remission
- Change from Baseline in duration of morning stiffness (in hours) by visit
- Change from Baseline in number of swollen and tender joints by visit (joint scores –TJC and SJC)
- Proportion of patients in clinical remission as defined by the ACR/EULAR 2011 remission criteria
- Employment status

- Employability due to RA
- Sick leave
- RA treatment following discontinuation of CZP

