5.1.1 Study duration

The entire study duration per patient is intended to be 116 weeks if not prematurely discontinued (see Section 6.3 for withdrawal criteria).

Intervals of visits:

- Baseline Visit at onset of therapy (after deciding to treat the patient with CZP).
 Note: A patient may be enrolled into the study after the start of CZP treatment if he/she met all inclusion and exclusion criteria at the start of CZP treatment. Written data consent must be obtained no later than the start of Visit 2 and prior to conducting any clinical assessment at Visit 2. Following written data consent (ie, enrollment into the study), all relevant data from original records will be entered onto study-specific forms.
- Frequent visits are expected around Weeks 6, 12, 24, 36, 52, 64, 76, and 104: evaluation of efficacy and safety by the treating physician.
- Safety Follow-Up Visit around Week 116.

Patients who stop CZP for lack of efficacy or safety reasons will be followed up for 84 days to analyze which treatments were commonly used after treatment failure of CZP.

Patients who discontinue CZP treatment due to personal reasons or as a result of the treating physician's decision will also be followed up for 84 days (except for patients who withdraw consent and cannot be followed up further).

The end of the study is defined as the date of the last visit of the last patient in the study.

It is anticipated that this study will be conducted from Q3 2009 to Q4 2014.

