6.3 Withdrawal criteria

Patients are free to withdraw from the study at any time without prejudice to their continued care.

If a patient discontinues for any reason, this reason must be recorded on the Study Completion Form. The physician will be encouraged to invite the patients who discontinue CZP therapy early to return to the clinic/practice for posttreatment. A Safety Follow-Up Visit will be performed 84 days after administration of the last dose of CZP.

In case a patient withdraws his/her data consent no further data should be collected or submitted on this patient or caregiver. If a patient is institutionalized, this should be recorded on the medical update form. Follow-up of hospitalized patients should continue during hospitalization. Hospitalization, by itself, does not necessarily constitute a reason for discontinuation.

The treating physician is free to add or withdraw any kind of medication, or to withdraw the patient from the study at his/her own discretion.

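### Treatment given after stopping CZP is analysed on a DAS28-dependent set, so stoppers without a valid post-Baseline DAS28 are left out

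*Protocol*

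**What the plan says.** Section 4.1.3 (Other efficacy variables) ends its list with "RA treatment following discontinuation of CZP". Section 12.1 then fixes the set without exception: "The analysis set for the efficacy variables will be the Full Analysis Set". Membership is limited to patients with a DAS28 of 2.6 or more "who took at least one dose of CZP and had at least one valid post-Baseline DAS28 value".

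The note in 12.1 gives the reason: "the Full Analysis Set is defined in this way because patients who had a Baseline DAS28 value <2.6 would already be in remission". It concludes: "Therefore, the primary efficacy variable to reach clinical remission would not be defined". The note says nothing about the post-Baseline condition or about any other variable.

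The wider set is described in the same section: "The analysis set for the safety variables will be the Safety Set (SS), which is defined as all patients who took at least one dose".

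Section 5.1.1 follows patients who stop for lack of efficacy or safety reasons for 84 days "to analyze which treatments were commonly used after treatment failure of CZP". It applies the same 84 days to stops for personal reasons or by the physician's decision. Section 6.3 requires the reason for discontinuing to be documented: "this reason must be recorded on the Study Completion Form".

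**The concern.** The variable asks what a patient received after CZP. Answering it needs a stop and a record of the next RA treatment. It needs no disease activity score. By filing it under efficacy, the protocol carries a filter built for the remission endpoint over to a variable for which that filter has no purpose.

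The loss is selective. The patients removed are those who stopped before any post-Baseline DAS28 was obtained, so they are drawn mainly from the quickest stops. If they go on to different treatments from patients who stop later, the tabulated treatment mix is shifted as well as based on fewer patients. The 84-day follow-up would have collected exactly the information wanted from them, and the analysis rule would then discard it.

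**Working it through.** **1. Can a patient have next-treatment data and still be outside the Full Analysis Set?**

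- First scheduled post-Baseline visit: around Week 6 (sections 5.1.1 and 5.2).
- Visit after an early stop: 84 days after the last treatment. Section 8.3 lists concomitant medication, adverse events and current RA treatment. It lists no joint counts, CRP or ESR, or patient global assessment, so a DAS28 cannot be calculated from that visit.
- DAS28 components are collected only where they belong to routine practice (footnote to 5.2; sections 8.1 and 8.2).

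A patient who stops before Visit 2 and has no other DAS28 therefore supplies the next treatment at the follow-up visit and fails the post-Baseline condition in 12.1. The exclusion follows from the text.

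**2. Does the stated rationale cover it?**

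The note in 12.1 justifies one condition (Baseline DAS28) for one variable (remission). The condition that removes these stoppers is the other one, and the variable is a different one.

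**3. How large could the loss be?**

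The protocol states no discontinuation rate and no rate of missing post-Baseline DAS28, so only a range under assumptions is possible. The one usable figure is the planned size in section 12.7, which reproduces: n = 1.96² × 0.5 × 0.5 / 0.03² = 1067.1, rounded up to 1068.

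Assume that all 1068 are treated. Let D be the share of treated patients who stop CZP, and q the share who stop with no valid post-Baseline DAS28. Then:

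- stoppers = 1068 × D
- stoppers lost from the Full Analysis Set = 1068 × q
- share of stoppers lost = q / D

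| D (stoppers) | q = 2% (21 lost) | q = 5% (53 lost) | q = 10% (107 lost) |
|---|---|---|---|
| 30% (320) | 2/30 = 6.7% | 5/30 = 16.7% | 10/30 = 33.3% |
| 50% (534) | 2/50 = 4.0% | 5/50 = 10.0% | 10/50 = 20.0% |

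The range is 4% to 33%. On the Safety Set the loss caused by the DAS28 conditions is zero.

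**4. Is the other discontinuation variable affected in the same way?**

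Section 4.1.3 also lists the incidence of stopping because of DAS28 (CRP) remission. Such a stop presupposes a post-Baseline DAS28, so the numerator stays and only the denominator shrinks. A 5% incidence on the Safety Set becomes 0.05 / 0.98 = 5.1% on the Full Analysis Set at q = 2%, and 0.05 / 0.90 = 5.6% at q = 10%. This variable needs no change.

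**The case against.** **Early stopping does not by itself exclude a patient.** This stands. What excludes is the absence of a valid post-Baseline DAS28. A patient who stops after a DAS28 at Visit 2 stays in, and section 8 accepts data from the visit nearest the scheduled time. Section 10.1.1 also mentions a Withdrawal Visit where applicable, which could supply a DAS28, although the schedule in 5.2 contains no such visit. A reader might infer that the earliest CZP failures drop out as a class. The protocol does not support that.

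**Stop reasons.** A reader might also infer that the analysis pools all reasons for stopping and so blurs the picture after treatment failure. The protocol does not say so. Section 12.3.2 says only that the analysis is descriptive, the reason is recorded, and table layout can be left to the SAP. The objective in section 3.3 covers any discontinuation, which matches the variable in 4.1.3. Treatment failure is one purpose named in 5.1.1, and other stops are followed as well. There is no contradiction on scope.

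**Other variables.** It is tempting to move every variable that does not use DAS28, such as sick leave and employment, off the Full Analysis Set. Those items are scheduled at Visits 1 to 9 and not at the Safety Follow-Up, so a patient who stops before Visit 2 with no later treatment-period visit has no post-Baseline value to add. Little would be gained for the patients at issue here.

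**The Safety Set does not recover everyone.** This also stands. Patients enrolled after starting CZP give consent at the latest at the start of Visit 2. Anyone on that route who stopped and never reached Visit 2 is in neither set.

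**Weight.** One common set for all efficacy tables is convenient, and all analyses are exploratory and descriptive (section 12.2). That limits the importance of the point. It gives no reason to apply the filter to a variable that does not use DAS28.

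**Conclusion.** The point holds in a narrow form. Sections 4.1.3 and 12.1 together place treatment after CZP discontinuation on a set that requires a valid post-Baseline DAS28. Stoppers without one are excluded although section 8.3 collects what the variable needs. Section 12.1 states this assignment outright and does not leave it to the SAP, so an SAP using another set would depart from the protocol.

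The size cannot be derived from the protocol. The range of 4% to 33% of stoppers rests entirely on the assumed 2% to 10% who stop without a post-Baseline DAS28 and the assumed 30% to 50% who stop overall. The upper end pairs the highest loss with the lowest stop rate, and the lower end does the reverse. The Baseline condition probably removes few patients, because inclusion criterion 3 requires moderate to severe active RA.

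Severity is minor. One descriptive variable under the other objectives is affected. The primary remission rate and its confidence interval are not.

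**What to change.** In section 12.1, add that RA treatment after discontinuation is analysed on all Safety Set patients who discontinued CZP, and carry the same wording into the SAP. Because 5.1.1 names treatment failure as a purpose of the follow-up, the table can also be shown by the stop reason on the Study Completion Form. That breakdown is a useful addition and does not correct an error.

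The cost is one sentence and no new data collection. The denominator of this table will differ from that of the DAS28-based tables, so it should be labelled.

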4 STUDY VARIABLES

4.1 Efficacy variables

4.1.1 Primary efficacy variable

Clinical remission at Visit 9 (around Week 104) (defined as DAS28 of <2.6).

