5.2 Schedule of study assessments

The schedule of study assessments by visit are presented below.

Assessments ^a	Treatment period ^b							Safety Follow -Up		
Visit	V1	V2	V3	V4	V5	V6	V7	V8	V9	V10
Week	0	6	12	24	36	52	64	76	104	116
Written Data Consent ^c	X	X								
Demographics / Medical History	X									
Presence of Rheumatoid Factor	X									
Presence of anti-cyclic citrullinated peptide antibodies	X									
RA history	X									
Concomitant Medication	X	X	X	X	X	X	X	X	X	X
Adverse Events		X	X	X	X	X	X	X	X	X
Drug administration	X	X	X	X	X	X	X	X	X	
Joint scores (TJC, SJC) (28 joint count)	X	X	X	X	X	X	X	X	X	
Acute phase reactant (CRP or ESR)	X	X	X	X	X	X	X	X	X	
Morning stiffness	X	X	X	X	X	X	X	X	X	
Patient's Global Assessment of Disease Activity (VAS)	X	X	X	X	X	X	X	X	X	
Physician's Global Assessment of Disease Activity (VAS)	X	X	X	X	X	X	X	X	X	

Confidential Page 18 of 89

Assessments ^a	Treatment period ^b							Safety Follow -Up		
Visit	V1	V2	V3	V4	V5	V6	V7	V8	V9	V10
Week	0	6	12	24	36	52	64	76	104	116
Arthritis pain VAS	X	X	X	X	X	X	X	X	X	
Fatigue Assessment Scale	X	X	X	X	X	X	X	X	X	
HAQ-DI	X	X	X	X	X	X	X	X	X	
EQ-5D	X	X	X	X	X	X	X	X	X	
Sick leave	X	X	X	X	X	X	X	X	X	
Employment status and employability due to RA	X	X	X	X	X	X	X	X	X	
Information on subsequent RA treatment										X

CRP=c-reactive protein; EQ-5D=Euro Quality of Life – 5Dimensions; ESR= erythrocyte sedimentation rate; HAQ-DI; Health Assessment Questionnaire-Disability Index; RA=rheumatoid arthritis; SJC=swollen joint count; TCJ=tender joint count; V=Visit; VAS=Visual Analogue Scale

Confidential Page 19 of 89

^a Only if assessed as per current clinical practice. Since this is a noninterventional study, no additional diagnostic or monitoring procedure will be applied.

b Visits are recommended to be quarterly.

Written data consent will be obtained before any data are collected on study-specific forms. Written data consent may be obtained after the start of CZP treatment if the patient met all inclusion and exclusion criteria at the start of CZP treatment. For these patients, written data consent must be obtained at the start of Visit 2 and prior to conducting any clinical assessment at this visit.

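### Requiring a post-Baseline DAS28 for the efficacy set removes early stoppers from the 2-year remission denominator and can overstate remission relative to all treated patients

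*Protocol*

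**What the plan says.** Section 12.1 settles the population for efficacy in one sentence: "The analysis set for the efficacy variables will be the Full Analysis Set". That set is "all patients with a DAS28 ≥2.6 who took at least one dose of CZP and had at least one valid post-Baseline DAS28 value". The note beneath makes clear that the 2.6 threshold refers to Baseline and explains it by saying that "patients who had a Baseline DAS28 value <2.6 would already be in remission". It gives no reason for the post-Baseline condition. The Safety Set has no such condition; it is the set "which is defined as all patients who took at least one dose of CZP".

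Other sections bear on who is lost:

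- **Section 5.2.** The first post-Baseline collection of DAS28 components is at Visit 2 (Week 6). The footnote to the schedule limits all assessments: "Only if assessed as per current clinical practice".
- **Sections 5.2 and 8.3.** The Safety Follow-Up collects concomitant medication, adverse events and RA treatment. It collects no joint counts, CRP or ESR, or patient global assessment.
- **Section 6.3.** The reason for discontinuation must be recorded.
- **Section 12.5.** The handling of dropouts and missing data is left to the SAP.
- **Section 12.7.** The planned 1068 patients are to estimate a 50% remission rate to within ±3.0 points.

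**The concern.** Membership of the efficacy set depends on something that happens after treatment starts. A patient who stops CZP in the first weeks, for intolerance or lack of effect, may never have a post-Baseline DAS28. The only later contact that the schedule provides would not supply one. Section 10.1.1 mentions a withdrawal visit where applicable, but the schedule in Section 5.2 contains none. Such a patient is treated and counted for safety, but is absent from the efficacy denominator.

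Deferring missing data to the SAP does not settle this. Section 12.1 fixes who is in the set, and a rule that counts missing values as failures acts only on patients in it.

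The study reports a single remission rate with a confidence interval and has no second arm in which the same exclusion would occur. If the excluded patients are mostly early failures, the rate describes a more favourable group than those who started CZP, and the interval will not show it.

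**Working it through.** **The plan's own figure.** Section 12.7 uses p = 0.50 and a half-width of 0.03 at 95% confidence. Then n = 1.96² × 0.50 × 0.50 / 0.03² = 1067.07 (computed with the unrounded normal quantile), rounded up to 1068. The stated number is reproduced. Section 5.1.2 shows that 1068 counts enrolled patients, not members of the Full Analysis Set.

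**Effect of the post-Baseline requirement.** Let d be the share of treated patients with Baseline DAS28 ≥2.6 who have no post-Baseline DAS28, and R the remission rate in the Full Analysis Set. If every excluded patient counts as not in remission:

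- rate among all such treated patients = R × (1 − d)
- overstatement = R × d

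The protocol does not give d. The values below are assumptions, shown for R = 50% (the planning value) and R = 30% (also assumed).

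| d | R = 50%: rate in all treated | Overstatement | R = 30%: rate in all treated | Overstatement |
|---|---|---|---|---|
| 5% | 0.50 × 0.95 = 47.5% | 2.5 points | 0.30 × 0.95 = 28.5% | 1.5 points |
| 10% | 0.50 × 0.90 = 45.0% | 5.0 points | 0.30 × 0.90 = 27.0% | 3.0 points |
| 15% | 0.50 × 0.85 = 42.5% | 7.5 points | 0.30 × 0.85 = 25.5% | 4.5 points |

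The overstatement reaches 3.0 points at d = 0.03 / 0.50 = 6% when R = 50%, and at d = 0.03 / 0.30 = 10% when R = 30%.

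These are upper bounds. Some excluded patients will still be on CZP and merely unmeasured, and some of those may be in remission.

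**Observed-case comparison.** The observed-case rate at Visit 9 is the number with Visit 9 DAS28 <2.6 divided by the number with a Visit 9 DAS28. A patient with no post-Baseline DAS28 appears in neither count, so the requirement changes that rate by 0 points.

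**Effect of the ≥2.6 Baseline cut on remission.** If a share g enters below 2.6, a proportion q of them is in remission at Visit 9, and p of the others is, removing them changes the rate by −g × (q − p). Under assumed values:

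- g = 2%, q = 70%, p = 50%: −0.02 × 0.20 = −0.4 points
- g = 5%, q = 70%, p = 30%: −0.05 × 0.40 = −2.0 points

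Whenever q exceeds p, the cut lowers remission.

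**Low disease activity (DAS28 ≤3.2).** If a share f enters at 2.6 to 3.2, with later rates p1 among them and p0 among the rest, the rate exceeds that in patients entering above 3.2 by f × (p1 − p0). Under assumed values:

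- f = 2%, p1 = 80%, p0 = 60%: 0.4 points
- f = 10%, p1 = 80%, p0 = 40%: 4.0 points

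**The case against.** The strongest reply is that the effect depends on choices not yet visible. Section 12.5 leaves missing data to the SAP. If the SAP analyses only observed Visit 9 values, the post-Baseline condition changes nothing. This stands, and it is why the point is that remission can be overstated, not that it is. It does not remove the point: an observed-case analysis omits the same patients, so it does not recover the rate among all treated either.

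Second, the primary variable in Section 4.1.1 is DAS28 below 2.6 at Visit 9, with no condition of still being on CZP. A patient who stopped early and switched could be in remission at Week 104, so a reader should not infer that the outcome of early stoppers is known. Counting them as not in remission is a choice of what to estimate. Section 3.1, which speaks of remission after 2 years of therapy, is consistent with that choice but does not state it.

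Third, one valid DAS28 at any of the eight visits from Visit 2 to Visit 9 is enough to enter the set, so the excluded share may be small.

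Two stronger readings are tempting, and the protocol supports neither:

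- **That the ≥2.6 cut also inflates remission.** It removes patients who already have the outcome and, if anything, lowers the rate.
- **That low disease activity is wrongly analysed** because patients entering at 2.6 to 3.2 already meet it. Section 4.1.3 defines it as a state by visit, not as newly reached, and the reason given for the cut concerns the primary variable only. Section 6.1 has no numerical DAS28 limit, but it still asks for moderate to severe, active RA, so this group may be small.

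**Conclusion.** The concern holds for the post-Baseline requirement only. Section 12.1 removes treated patients without a post-Baseline DAS28 from the efficacy denominator, gives no reason for doing so, and leaves the SAP no means of restoring them within that set. Relative to all treated patients with Baseline DAS28 ≥2.6, the remission rate can be overstated by at most 2.5 to 7.5 points at a reported 50%, or 1.5 to 4.5 points at 30%. These figures assume that 5% to 15% are excluded and that none of them remit; neither assumption comes from the protocol. Relative to an observed-case Visit 9 analysis the effect is zero. The defect in the definition is clear, but its size is not known. The low-disease-activity question is one of presentation.

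**What to change.** In Section 12.1, define the efficacy set as patients with Baseline DAS28 ≥2.6 who took at least one dose of CZP. For the primary analysis:

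- count patients who stopped CZP before any post-Baseline DAS28 as not in remission;
- handle patients still on CZP but unmeasured under the SAP's missing-data rule;
- report the current definition as a sensitivity analysis, and state how many patients it excludes and why.

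If the sponsor prefers to keep the current set as primary, the minimum is to add the all-treated version as the sensitivity analysis.

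No new data are needed, because Section 6.3 already requires the reason for discontinuation. The cost is a wording change, one extra table and possibly a lower reported rate. A row for low disease activity in patients with Baseline DAS28 above 3.2 may be added for information, but it is optional.
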